Subjects will be randomized to active Naltrexone 25mg, Naltrexone 50mg, and placebo groups in a 1:1:1 ratio using a computer randomization procedure at the CMHC research pharmacy, blind to both research team and subjects. Separate randomization schedules will be applied based on gender, and antipsychotic agent to yield an equal number of male and female subjects in each arm. This is to control for possible differential gender and racial/ethnicity specific effects of Naltrexone on weight as well as differences brought on by higher and lower weight liability medications.

Subjects will take the study medication daily for 52 weeks. Subjects will be seen weekly for the first 4 weeks of the study, thereafter they will be seen on a bi-weekly (every other week) basis to be assessed (i.e. weight, side effect check, paper questionnaires) throughout the remaining 48 weeks of treatment. Compliance will be monitored by pill counts as well as 25mg riboflavin added to the capsules which provides florescence to urine under Wood's lamp (UV or black light). Subjects will be given a study identification card listing the fact that they may be taking naltrexone and this card will include the study emergency cell phone number which will be available 24 hours a day, 7 days per week in case of an emergency.

The study is planned to be run at the Connecticut Mental Health Center (CMHC) and its affiliated satellite clinics throughout the greater New Haven area.

All participants will be carefully assessed with physical examination and laboratory findings, any medical problems that need immediate attention will be referred to each participant's own primary care physician. All potential subjects will meet with study staff for intake and evaluation sessions to determine eligibility prior to enrollment.

A description of assessments is given below:

1) Intake interview including demographics, clinical history, Structured Clinical Interview for DSM-IV (**SCID**) to ascertain diagnosis. 2) Urine toxicology (**Utox**) screen to rule out substance use. The initial sample will also be sent to the lab to confirm opiate results for safety purposes and a follow-up sample will be taken immediately before randomization to study medication to ensure it is negative for opiates; continued random testing will occur at the discretion of the study physician throughout the trial along

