Data will be electronically scanned into databases and will be double checked by hand. Hard copy documents will be examined to verify questionable observations. Missing data will be examined for each variable. Histograms, normal probability plots, and numerical summaries (skewness, kurtosis) will be used to examine distributional assumptions required for the mixed model analysis described below. Transformations such as the logarithm, square root, and reciprocal will be considered in the event the normality assumption is inadequate. Residual analysis will also be performed to evaluate distributional variance and linearity assumptions. Data analysis will be conducted in collaboration with [name], statistician in the department of Psychiatry and [name] faculty member of the Department of Biostatistics at Yale University School of Public Health. For all analyses, an alpha threshold of 5% (two-sided) will be used to test for statistical significance and will be performed using SAS v9.3 (SAS Institute, Cary, NC).

Analyses will be performed according to the intent-to-treat (ITT) principle where data from any randomized subjects will be analyzed. We will calculate descriptive statistics for participants at baseline, and compare naltrexone to placebo participants using analysis of variance (ANOVA) for normally distributed covariates and chi-square tests for categorical covariates. The impact of baseline variables that demonstrate clinically relevant group differences will be assessed in supportive analyses using covariate adjustment.

Approach to Missing Data: The primary analysis method will use a likelihood-based mixed model, which accommodates incomplete observations and operates under the assumption that the missing data is missing at random (MAR). Missing data patterns, time to withdrawal and reasons for dropout will be compared between the two naltrexone and placebo groups. T-tests, cross-tabulations, and logistic regression will be used to evaluate whether withdrawal is dependent on any observed variables. Finally, should missing data patterns and reasons for missing data suggest a bias or confounding, we will conduct sensitivity analyses using pattern mixture models to examine the influence that dropout bias (informative missingness) may have on treatment differences. Multiple imputation (MI) will also be used in the case of data not MAR. Sensitivity analyses will be performed secondarily among study completers.

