Hypothesis Testing: The primary goal of this study is to compare the weight changes resulting from two different doses of naltrexone compared to placebo. The primary ITT analysis will employ a linear mixed effects model (LMM) to determine the effect of treatment status (between-subjects for: naltrexone 25/50mg vs. placebo) on the trajectory of weight change over time (within-subjects for: study time points). The interaction between treatment and time will be modeled and interpreted using graphical displays and post-hoc contrasts on least square means. The latter will include estimation of group contrasts at each time point and polynomial (linear, etc.) contrasts for time within each group. However, the primary contrasts will be each dose compared with control at 52 weeks. Because the outcome data are correlated (i.e., weight assessed from the same subject at different time points), weight over time will be modeled through the inclusion of random subject effects and/or structured variance-covariance matrices, with the best-fitting structure determined by Bayesian-Schwartz Information criteria (BIC). Supportive analyses will also include covariate adjustment for clinically significant variables (as determined from baseline evaluations and also other treatment variables, such as sessions attended). The above model will be fit using SAS PROC MIXED (Cary, NC), using restricted maximum likelihood (REML). The effect of treatment assignment on the secondary outcomes, such as BMI, waist circumference, serum lipid profile, fasting glucose, and glycosylated hemoglobin (HbA1c) will be evaluated using the linear mixed modeling approach described above. The proportion of subjects achieving 3, 4, or 5% weight loss will be compared between the treatment groups with the Fisher's Exact test. Type 1 error for secondary outcomes will be adjusted using the Bonferroni correction, basing the adjustment on the number of conceptually related statistical tests.

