SECTION VII: RECRUITMENT/CONSENT AND ASSENT PROCEDURES

1. Targeted Enrollment: Give the number of subjects:

a. targeted for enrollment at Yale for this protocol 200

b. If this is a multi-site study, give the total number of subjects targeted across all sites N/A

2. Indicate recruitment methods below. Attach copies of any recruitment materials that will be used.

- Flyers
- Posters
- Letter
- Medical Record Review
- Departmental/Center Newsletters
- YCCI Recruitment database
- Other (describe): Clinician Referrals

- Internet/Web Postings
- Mass E-mail Solicitation
- Departmental/Center Website
- Departmental/Center Research Boards
- Web-Based Clinical Trial Registries
- Clinicaltrials.gov Registry (do not send materials to HIC)

- Radio
- Telephone
- Television
- Newspaper

3. Recruitment Procedures:

a. Describe how potential subjects will be identified.

Potential subjects will either self-identify by seeing a flyer and contacting us with their interest, or their clinician may identify them as potentially eligible and give them our contact information. Familiar patients who have done multiple studies with us or who are patients of [name] may be identified by research staff as potentially eligible.

b. Describe how potential subjects are contacted.

Potential subjects will contact research staff in order to complete a telephone screening procedure that will determine eligibility. At that point, we will get permission from the patient to contact them further about the study, via telephone or through their clinician. If a potential subject has been in one of our studies in the past and has given permission to be contacted about future studies, research staff will call them to see if they are interested.

c. Who is recruiting potential subjects?

[name], [name], [name], [name], [name], [name]

4.

Screening Procedures

- a. Will email or telephone correspondence be used to screen potential subjects for eligibility prior to the potential subject coming to the research office? Yes No
- b. If yes, identify below all health information to be collected as part of screening and check off any of the following HIPAA identifiers to be collected and retained by the research team during this screening process.

HEALTH INFORMATION TO BE COLLECTED:

HIPAA identifiers:

- Names

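### The 3, 4 and 5% weight-loss comparison uses an unstratified Fisher's exact test with no rule for missing weights: valid, but less efficient than it need be and not fully specified

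*Combined protocol and SAP*

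**What the plan says.** The responder comparison takes one sentence in the Hypothesis Testing paragraph of Section V, item 12 (Statistical Considerations): "The proportion of subjects achieving 3, 4, or 5% weight loss will be compared between the treatment groups with the Fisher's Exact test". That sentence gives no time point. It does not say whether the comparison is one three-group test or two dose-versus-placebo tests, and it gives no rule for a subject whose weight is missing. Week 52 is named only for the primary mixed-model contrasts on weight.

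The surrounding rules are these:

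- Level: "an alpha threshold of 5% (two-sided) will be used to test for statistical significance".
- Multiplicity: "Type 1 error for secondary outcomes will be adjusted using the Bonferroni correction". The divisor is left to the number of related tests.
- Population: "Analyses will be performed according to the intent-to-treat (ITT) principle where data from any randomized subjects will be analyzed".
- Randomisation (Section V, item 3, Research Plan): "Separate randomization schedules will be applied based on gender, and antipsychotic agent". The stated reason is to control for differential effects on weight. No analysis text names these factors.
- Missing data (Approach to Missing Data paragraph): the primary tool is a likelihood-based mixed model under missing at random (MAR). Pattern-mixture models and multiple imputation are conditional, and a completers analysis is secondary. None is tied to the responder outcome.

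**The concern.** Two things are at stake.

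The first is efficiency. Fisher's test conditions on the total number of responders, so at this sample size its attainable error rate sits well below the nominal level. It also takes no account of the randomisation factors. When allocation is balanced within strata that predict outcome, an unadjusted test overstates the variance and becomes more conservative still.

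The second is specification. The test needs a yes or no for every subject it includes. The mixed model handles missing weights through the likelihood of the repeated measurements and assigns no responder status to anyone. The plan brings in multiple imputation only if the data are judged not MAR, so under its own primary assumption nothing says how a leaver is classified. In a 52-week trial some loss is foreseeable, and the rule would then be chosen with the data in view. Responder proportions are easy for clinicians to read, so a result that depends on an unwritten rule matters even for a secondary outcome.

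**Working it through.** The documents give no responder rates, dropout rate or power calculation for this outcome, so there is no planned figure to reproduce. Responder rates, dropout and stratum effects below are assumptions, shown over a range.

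**Inputs from the documents.** Section VII, item 1: "targeted for enrollment at Yale for this protocol 200". Section V, item 3: "placebo groups in a 1:1:1 ratio using a computer randomization procedure". Hence 200 / 3 = 66.7, or 66 to 67 per arm. Alpha is 0.05 two-sided.

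**Step 1: true size.** Enumerate every 2×2 table with n per arm. With a common rate p, size = Σₐ Σ_b Bin(a; n, p) · Bin(b; n, p) · 1{test p-value ≤ 0.05}.

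| Common rate (67 per arm) | Fisher | Pearson chi-square |
|---|---|---|
| 10% | 0.024 | 0.051 |
| 20% | 0.031 | 0.049 |
| 30% | 0.033 | 0.050 |
| 40% | 0.032 | 0.047 |
| 50% | 0.031 | 0.047 |

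At 66 per arm the sizes are 0.0285 versus 0.0481 at 15%, and 0.0315 versus 0.0492 at 25%.

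**Step 2: power.** Use the same sum with different rates in the two arms.

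| Rates (active v placebo) | n per arm | Fisher | Chi-square | Gap (points) |
|---|---|---|---|---|
| 30 v 10% | 67 | 79.2% | 84.4% | 5.2 |
| 35 v 15% | 66 | 70.7% | 76.8% | 6.1 |
| 40 v 20% | 67 | 66.1% | 72.4% | 6.3 |
| 45 v 20% | 67 | 84.5% | 88.4% | 3.9 |
| 50 v 30% | 67 | 59.0% | 65.4% | 6.4 |

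Under Bonferroni the gap for 40 v 20% is slightly larger. At 0.05/3 it is 49.1% versus 56.1% (7.0 points). At 0.05/6 (three thresholds, two doses) it is 39.6% versus 46.5% (6.9 points). Both divisors are illustrative.

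**Step 3: using the strata.** Simulation of 3,000 trials, 67 per arm, four near-equal strata balanced between arms. Rates at the centre of the log-odds scale are 20% and 40%. Fisher is compared with the Cochran-Mantel-Haenszel (CMH) test.

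| Stratum effect (log-odds span) | Fisher power | CMH power | Fisher size | CMH size |
|---|---|---|---|---|
| None (0) | 67% | 73% | 0.032 | 0.051 |
| Moderate (1.5) | 61% | 70% | 0.023 | 0.048 |
| Strong (3.0) | 48% | 65% | 0.021 | 0.052 |

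With no stratum effect, the gap is simply Fisher's conservatism. It widens as the strata become more predictive, while CMH keeps its size near 5%.

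**Step 4: the missing-weight rule.** Assume true rates of 20% (placebo) and 40% (naltrexone), and that leavers would have responded at the same rates. Completers only then gives 0.40 − 0.20 = 0.20 throughout. Counting leavers as failures gives 0.40(1 − d₁) − 0.20(1 − d₀), where d₁ and d₀ are dropout on naltrexone and placebo.

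| Dropout placebo / naltrexone | Leavers as failures |
|---|---|
| 20% / 20% | 0.32 − 0.16 = 0.16 |
| 30% / 30% | 0.28 − 0.14 = 0.14 |
| 40% / 40% | 0.24 − 0.12 = 0.12 |
| 20% / 40% | 0.24 − 0.16 = 0.08 |
| 40% / 20% | 0.32 − 0.12 = 0.20 |

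The same trial can therefore report 20 points or 8, depending on a rule that the plan does not state.

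**The case against.** The best defence is that nothing here is invalid. Fisher's test holds its type I error, whereas chi-square does not always do so: at 47 per arm (an assumed 30% loss) with 10% responders, its size is 5.9%. The outcome is secondary, and the primary inference rests on the mixed model. All of that stands. It limits the weight of the point but does not remove it, because a stratum-adjusted analysis recovers the lost power at little cost.

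Several stronger readings are tempting, and the documents do not support them.

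- *Fisher's test cannot include subjects without a week-52 weight.* It can, once a status is assigned by a failure rule, an earlier weight or imputation. What is missing is the rule.
- *The mixed model is the plan's only tool for missing data.* Pattern-mixture, multiple imputation and completers analyses are also listed. They are conditional or secondary, and are not connected to this outcome.
- *The responder analysis contradicts intention to treat.* Nothing restricts it to completers. Silence is not a contradiction, and counting leavers as failures keeps everyone randomised.
- *The test ignores baseline weight.* Percentage loss is already scaled to baseline. The pilot described in Section V, item 2 also found no correlation between baseline weight and weight change, so the documents give little reason to expect much gain from that covariate.

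Covariate adjustment is planned in general terms, but as supportive work and without naming the strata. The generalised mixed models that allow binary data are listed under Other Outcomes.

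**Conclusion.** The point holds as one of efficiency and specification. At 66 to 67 per arm Fisher's test runs at about 2.4 to 3.3% true size and loses about 4 to 6 points of power at the unadjusted 5% level, for assumed rates between 10% and 50%. Leaving out the randomisation factors adds a further loss whose size depends on how strongly gender and antipsychotic agent predict response. The documents do not give that, and the simulated range is illustrative.

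The missing-weight rule may matter more. With the assumed rates, the two obvious rules differ by 0 to 12 points over the dropout patterns examined. A reader might infer that the result will be biased, but that cannot be claimed. Under the assumption used here completers only is unbiased, and under other mechanisms the direction and size of any bias depend on dropout behaviour that the documents do not describe. What can be said is that the answer depends on an unstated choice. The change should be made, at the priority of a secondary analysis.

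**What to change.** Replace the responder sentence in the Hypothesis Testing paragraph with text that does the following:

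- Compare each dose with placebo at week 52, matching the primary contrasts, by logistic regression (or a CMH test) using the randomisation strata. If strata by individual agent are sparse, group the agents by the weight-liability ranking already cited under Other Outcomes. Baseline weight may be added but is optional.
- Multiply impute missing week-52 weights from the weekly and two-weekly weights in the Assessment Schedule, then derive responder status. Do this as the main approach for this outcome, not only if data are judged not MAR.
- Report leavers as failures as a sensitivity analysis.
- Keep all three thresholds under the planned Bonferroni correction and state the divisor. Section IX rests the expected benefit on a 4% loss, so that threshold should not be demoted.

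The cost is a few lines of analysis-plan wording and modest programming. No extra data are needed. The downside is reliance on the imputation model, which the sensitivity analysis helps to check.

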with medication compliance procedures; and pregnancy tests for female subjects as it may not be advisable for pregnant women to lose weight. 3) Weight (**Wt**) measurement to the nearest 0.5kg and height (**ht**) will be measured to calculate **BMI**. Waist circumference (**WC**) will be measured with a tape measure placed on the midpoint between iliac crest and lowest rib rounded to the nearest 5 mm. Resting blood pressure (**bp**) and pulse will be measured. Our lab has established procedures for calibrating scales (National Institutes of Standards and Technology Certified weights) and waist measurement. The lab conducts reliability exercises for waist measurements for study stuff (ICC= 0.97, TEM=2.4%) 4) Standard Laboratory Testing (**Lab**) 5) Brief Psychiatric Rating Scale (**BPRS**) is the gold-standard overall measure of schizophrenia symptoms which will be utilized to demonstrate that the Naltrexone and/or SIMPLE intervention does not cause worsening of the illness symptoms apart from the usual fluctuations of the natural course. 6) Beck Depression Inventory (**BDI**) 21-item version is a psychometrically sound, widely used measure of the features and symptoms of depression. The BDI taps a broad range of negative affect – not just depression – and is a highly efficient measure for detecting fluctuations in broad psychopathology and distress. 7) Three Factor Eating Questionnaire (**TFEQ**) also known as the Eating Inventory is a measure of eating behaviors with three factors: dietary (cognitive) restraint, disinhibition, and hunger. The TFEQ has received psychometric support and is a frequently used measure in obesity trials. 8) The Questionnaire on Craving for Sweet or Rich Foods (**QCSR**) The QCSR is a two factor, nine item scale assessing the presence of cravings for rich and sweet foods and has been found to have good psychometric properties. 10) The Yale Physical Activity Survey (**YPAS**) is an interview-administered questionnaire that assesses activity participation in number of hours/week in different categories (i.e. work, recreation, exercise) and takes about 20 minutes to complete. 11) Resting Metabolic Rate (**RMR**) is calculated through a mathematical formula not indirect calorimetry. No special procedure is utilized that would be bothersome to subjects. 12) Quality of Life Enjoyment and Satisfaction Questionnaire (**Q-LES-Q**) is specifically designed to use with schizophrenia patients and focuses on patient's subjective perception of various aspects of their life. 13) SF-36 Health related Quality of Life Questionnaire; a 36-item short-form (**SF-36**) was constructed to survey health status in the Medical Outcomes Study. The SF-36 was designed for use in clinical practice and research, health policy evaluations, and general population surveys. The SF-36 includes one multi-item scale that assesses eight health concepts: 1. limitations in physical activities because of health problems; 2. limitations in social activities because of physical or emotional problems; 3. limitations in usual role activities because of physical health problems; 4. bodily pain; 5. general mental health (psychological distress and wellbeing); 6. limitations in usual role activities because of emotional problems; 7. vitality (energy and fatigue); and 8. general health perceptions. SF-36 can be administered as a self-rating scale or by interviewer. In this study, trained rates will administer the SF-36. 14) UKU Side Effect Checklist (**UKU**) This is a comprehensive rating scale developed for psychotropic drugs and a cross-sectional study of side effects in neuroleptic-treated patients. Common adverse events related to naltrexone will be added to this scale, as needed. 15) Columbia-Suicide Severity Rating Scale (**C-SSRS126**) is a scale developed for use in clinical trials of psychoactive agents and recommended by the FDA to be used for safety tracking of medications for suicidality. 16) Cognitive Battery. Tests from the Measurement and Treatment Research to Improve Cognition in Schizophrenia (**MATRICS**) Consensus Cognitive Battery (**MCCB**): Given the cognitive impairment of schizophrenia, careful assessment of cognition is necessary for feasibility of any medication use in schizophrenia. This is a cognitive battery developed on NIMH initiative by experts from academia, pharmaceutical industry, and US government for the specific purpose of use in clinical trials in schizophrenia. Validity, reliability, sensitivity to change, and normative data is established.

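### Secondary outcomes: replace single-step Bonferroni with Holm, inside families of tests that are fixed before unblinding

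*Combined protocol and SAP*

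**What the plan says.** All references are to the combined protocol and SAP.

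- **Significance level** (Section V, item 12, opening paragraph): "For all analyses, an alpha threshold of 5% (two-sided) will be used to test for statistical significance".
- **Method** (same item, Hypothesis Testing): "Type 1 error for secondary outcomes will be adjusted using the Bonferroni correction", "basing the adjustment on the number of conceptually related statistical tests". No number, list of tests or date of fixing follows.
- **Outcomes covered** (same paragraph): BMI, waist circumference, lipid profile, fasting glucose and HbA1c. They are given as examples, so the list is open, and the lipid fractions are not named.
- **Responder analysis** (same paragraph): "The proportion of subjects achieving 3, 4, or 5% weight loss will be compared between the treatment groups". Whether these tests count towards the correction is not stated.
- **Contrasts**: for weight, "the primary contrasts will be each dose compared with control at 52 weeks". The secondary outcomes use the same model, but their contrasts and time point are not spelled out.
- **Hypotheses** (Section V, item 1): Hypothesis 1 groups BMI and waist circumference with weight. Hypothesis 2 holds the lipids, glucose and HbA1c.
- **BMI** (Section V, item 3, assessments): it is calculated from weight "measurement to the nearest 0.5kg and height".

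**The concern.** Two features cost something that the plan need not pay.

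First, single-step Bonferroni holds every test to the strictest threshold, even after other tests in the family have been rejected. Holm starts at that threshold and relaxes it after each rejection, with the same family-wise guarantee under any correlation.

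Second, the divisor is not defined. Until it is, nobody can state the significance level for any lipid, glucose or HbA1c test, and Hypothesis 2 rests on those tests.

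A smaller matter is BMI. In an adult it is weight divided by a constant, so a formal BMI test nearly repeats the primary question and uses error in whichever family holds it.

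**Working it through.** The plan gives no divisor, adjusted level or power for the secondary outcomes, so there is no stated figure to reproduce.

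**Inputs from the documents.** 200 subjects randomized 1:1:1, so n = 200/3 = 66.7 per arm; two-sided 5% level.

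**Assumed inputs.** Two dose contrasts per secondary outcome; standardized effects d of 0.2 to 0.59; correlation 0.3 between outcomes; no dropout. The only effect size in the documents is the pilot's d = 0.59, for weight at 8 weeks.

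**Step 1: divisors that the text allows.**

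- Each outcome as its own family: 1 × 2 doses = 2
- BMI and waist: 2 × 2 = 4
- Five named outcomes: 5 × 2 = 10
- Lipids counted as four fractions (assumed): 8 × 2 = 16
- Plus three responder thresholds: 16 + 3 × 2 = 22

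**Step 2: level and power per test under Bonferroni.** The level is 0.05/m. Power ≈ Φ(d√(n/2) − z), where z is the upper 0.025/m normal quantile. For d = 0.5 and m = 10: 0.5 × √33.3 = 2.887, z = 2.807, and Φ(0.080) = 53%.

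| m | level per test | d = 0.4 | d = 0.5 | d = 0.59 |
|---|---|---|---|---|
| 2 | 0.0250 | 53% | 74% | 88% |
| 4 | 0.0125 | 43% | 65% | 82% |
| 10 | 0.0050 | 31% | 53% | 73% |
| 16 | 0.0031 | 26% | 47% | 67% |
| 22 | 0.0023 | 23% | 43% | 64% |

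The level varies 11-fold (22/2). If divisor 2 were used throughout, the error over ten independent tests would be 1 − 0.975^10 = 22%. With divisor 10 it is at most 5%.

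**Step 3: Holm against Bonferroni.** Holm orders the p-values and compares the i-th smallest with 0.05/(m − i + 1), stopping at the first failure. The first threshold is Bonferroni's and the later ones are larger, so Holm never rejects less. The table comes from simulation: 40,000 trials, shared placebo arm, 66 to 67 per arm. It shows average power over the responding tests, except that the m = 10 row with two responders is for waist at one dose.

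| Tests | Which outcomes respond | Bonferroni | Holm | Gain (points) |
|---|---|---|---|---|
| 8 | all, d = 0.2 | 5.7% | 6.2% | 0.5 |
| 8 | all, d = 0.3 | 15.6% | 18.2% | 2.6 |
| 14 | all, d = 0.3 | 11.7% | 13.2% | 1.5 |
| 8 | one of four, d = 0.5 | 55.1% | 56.1% | 1.0 |
| 14 | two of seven, d = 0.5 | 47.9% | 49.3% | 1.4 |
| 10 | two of five, d = 0.5 | 52.9% | 55.2% | 2.3 |
| 8 | all, d = 0.5 | 55.6% | 67.3% | 11.7 |
| 10 | all, d = 0.5 | 53.2% | 65.1% | 11.9 |

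With no true effects, the two methods had the same family-wise error (4.7% with ten tests).

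**Step 4: BMI.** With an assumed mean height of 1.68 m (SD 0.07 to 0.10 m) and a weight-change SD of 6 kg, BMI change and weight change correlate at about 0.99. Their 5% tests agreed in 97 to 99% of simulated trials. The effect of removing BMI at d = 0.5 under Bonferroni depends on the family:

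- Hypothesis 1 family (BMI and waist): m falls from 4 to 2, and power for waist rises from 65% to 74%.
- Hypothesis 2 family: BMI is not in it, so nothing changes.
- One pooled family of five outcomes: m falls from 10 to 8, and power rises from 53% to 56%.

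**The case against.** Bonferroni is valid. It protects the family: ten unadjusted independent tests would carry 1 − 0.95^10 = 40% error. It also comes with simple matching simultaneous confidence intervals, which Holm lacks. Preferring Holm is therefore a gain in efficiency and does not correct an error. All of this stands. A reader who concludes that the plan throws power away for nothing goes too far; only the Holm increment and any BMI share are avoidable.

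The gain may also be small. About 12 points requires every secondary outcome to respond by 0.5 SD at both doses. The documents give no effect size for any of these outcomes, and Section V, item 7 excludes treated diabetes and confirmed HbA1c above 7, so effects of that size on glucose and HbA1c are a strong assumption. This stands too, and is why the gain is given as a range.

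Two further inferences are tempting but not supported. A reader might infer that the divisor will be picked once results are known. The text is silent on timing; that permits such a choice but does not say it will happen, and the open divisor is mainly missing detail. A reader might also infer that BMI makes the tests of lipids, glucose and HbA1c stricter. Section V, item 1 places BMI under Hypothesis 1, and nothing puts it in a family with those markers.

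**Conclusion.** The point holds as an improvement to the secondary analysis. The primary contrasts are not affected. Holm controls the same error and cannot reject less. The expected benefit is about 1 to 3 points of average power if effects are small or few outcomes respond (as little as 0.5 at 0.2 SD), and about 12 points if all respond by 0.5 SD. These figures rest on assumed effects, about 67 per arm, correlation 0.3 and no dropout; dropout would lower every power figure.

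The families need to be written down for either method to have a defined level, since the present wording allows 2 to about 22 tests. Treating BMI as supportive is justified because it carries almost no information beyond weight. Under the hypothesis-based grouping, the benefit goes to waist circumference alone.

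**What to change.** Amend the Hypothesis Testing paragraph before unblinding:

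1. Replace Bonferroni with Holm at two-sided 5% within each family.
2. Family (a), Hypothesis 1: waist circumference, each dose against placebo at week 52 (2 tests).
3. Family (b), Hypothesis 2: each lipid fraction, listed by name, with fasting glucose and HbA1c, each dose against placebo at week 52. With four fractions this is 6 × 2 = 12 tests.
4. State whether the 3, 4 and 5% responder comparisons form a family of their own or are supportive.
5. Report BMI as supportive, beside weight.
6. Report unadjusted confidence intervals, labelled as such, beside the Holm-adjusted p-values.

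Waist should stay out of family (b). If lipids counted as one outcome, adding waist would raise m from 6 to 8 and lower Bonferroni power at d = 0.5 from 60% to 56%, about what BMI costs in a pooled family.

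The cost is SAP wording, with no new data, visits or subjects. BMI loses a formal test that weight already supplies, and simple simultaneous intervals are given up. Error is controlled within each family, so over (a) and (b) together it is bounded by 2 × 5% = 10%; the plan should say that this is intended.
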